#### **6.1.2. Medical Devices**

The combination products provided for use in the study are the tirzepatide prefilled syringe and placebo prefilled syringe.

Product complaints (including malfunction, use error, and inadequate labeling) shall be documented and reported by the investigator throughout the clinical investigation and appropriately managed by the sponsor (see Section 10.3.3).

### **6.2. Preparation, Handling, Storage, and Accountability**

The investigator or designee must confirm that appropriate storage conditions have been maintained during transit for all study intervention received and any discrepancies are reported and resolved before the use of the study intervention.

Only participants enrolled in the study may receive study intervention. Only authorized study personnel may supply, prepare, or administer study intervention. All study intervention must be stored in a secure, environmentally controlled, and monitored (manual or automated) area in accordance with the labeled storage conditions with access limited to the investigator and authorized study personnel.

The investigator or authorized study personnel are responsible for study intervention accountability, reconciliation, and record maintenance (that is, receipt, reconciliation, and final disposition records).

All used or unused study drugs may only be destroyed by the site at the end of the study upon complete reconciliation and receipt of written authorization by the sponsor or its designee.

### **6.3. Measures to Minimize Bias: Randomization and Blinding**

This is a participant- and investigator-blinded study. To preserve the blinding of the study for tirzepatide and placebo, all study site personnel, except staff who prepare and dispense study intervention, will be blinded to treatment allocation.

All participants will be centrally assigned to randomized study intervention using an Interactive Web Response System. Before the study is initiated, the log-in information and directions for the Interactive Web Response System will be provided to each site.

Study intervention will be dispensed at the study visits summarized in SoA.

Returned study intervention should not be re-dispensed to participants.

If a participant's study treatment assignment is unblinded, the participant must be discontinued from the study, unless the investigator obtains specific approval from a sponsor CP or CRP for the study participant to continue in the study. During the study, emergency unblinding should occur only by accessing the study participant's emergency code.

In case of an emergency, the investigator has the sole responsibility for determining if the unblinding of a participant's treatment assignment is warranted for the medical management of the event. The participant's safety must always be the first consideration in making such a determination. Where feasible and when timing of the emergent situation permits, the investigator should attempt to contact the Lilly medical monitor before unblinding a participant's treatment assignment. If the investigator decides that unblinding is warranted, it is the responsibility of the investigator to promptly document the decision and rationale and notify the sponsor as soon as possible.

Upon the completion of the study, all codes must be returned to the sponsor or its designee.

### **6.4. Study Intervention Compliance**

When participants are dosed during outpatient visits at the CRU, study intervention will be administered under medical supervision by the investigator or designee. The dose of study intervention and study participant identification will be confirmed prior to the time of dosing. The date and time of each dose administered will be recorded in source documents and will be provided to the sponsor as requested.

Self-administration by a participant or parent or legal guardian is permitted after the investigator has assessed them as being adequately trained. When administered at home, dosing information will be recorded in study dosing records provided by the investigator and compliance with study intervention will be assessed at each visit via review of dosing records and returned used prefilled syringes. Compliance will be further assessed by direct questioning and documented in the source documents and CRF.

A record of the number of study intervention prefilled syringes dispensed to and taken by each participant must be maintained and reconciled with study intervention and compliance records. Intervention start and stop dates, including dates for intervention delays, will also be recorded in the CRF.

## 6.5. Dose Modification

Dose modification other than that defined per protocol is not permitted in this study.

In certain situations, after randomization, for example, if GI tolerability AEs occur, the investigator may need to temporarily interrupt treatment. Investigators should preferably consult with and notify the sponsor CP/CRP, if treatment needs to be interrupted. Every effort should be made by the investigator to maintain participants on treatment and to restart treatment after temporary interruption, as soon as it is assessed as safe to do so. The participant should resume study treatment administration at the scheduled dose level per protocol.

If any of the following scenarios occur, dosing at the current level and further dosing will be stopped for the participant who will be discontinued:

1. The SAE is considered at least possibly related to the study intervention.
2. A severe non-serious AE occurs and is considered at least possibly related to the study intervention occurring in the participant.
3. The participant experiences intolerable GI events that require further dose interruptions, and the investigator or designee determines that it is unsafe to resume continued treatment.

If any of the following scenarios occur, an additional safety review will be initiated and new enrollment will be paused until the safety review is complete:

1. One or more participants in the cohort on active drug experience SAE considered to be related to tirzepatide.
2. One or more participants on active drug experience 2 clinically significant severe AEs considered to be related to tirzepatide.
3. Two or more participants in the cohort experience
  - a. drug-related GI effects (for example, emesis and diarrhea) assessed to be severe treatment-emergent AEs causing significant distress or requiring urgent medical interventions beyond routine symptomatic treatment, and
  - b. symptomatic hypoglycemic episodes with blood glucose levels of <3.0 mmol/L (54 mg/dL).

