## 4. Study Design

### 4.1. Overall Design

This is a randomized, placebo-controlled, participant and investigator blinded, 8-week treatment Phase 1 study in pediatric participants with obesity who do not have diabetes mellitus. Potential pediatric participants will be screened to assess their eligibility to enter the study within 28 days prior to Day 1. Participants enrolled will be partitioned as follows:

- Cohort 1: Higher weight cohort – screening body weight  $\geq 50$  kg
- Cohort 2: Lower weight cohort – screening body weight  $< 50$  kg, and
- Cohort 3: Screening body weight between 40 to 60 kg, inclusive.

The schematic of the study is shown in [Figure GPHV.1.1](#). Initially, [redacted] participants are planned to be enrolled into the higher body weight (Cohort 1). Participants will be randomized on Day 1 to tirzepatide or placebo ([redacted] ratio) after the confirmation of eligibility. Placebo is included as the control in a blinded manner for investigator, site staff, and participants to allow an unbiased assessment of the safety and tolerability data generated, which will allow a more robust comparison between tirzepatide and placebo. In-clinic outpatient visits are planned as detailed in the SoA.

Safety and tolerability data will be reviewed by the unblinded sponsor CP, CRP/CRS, and blinded investigator. Decisions for commencing dosing in Cohort 2 (lower body weight participants) will be made based on the following:

- the completion of at least 5 treatment doses from at least [redacted] participants in Cohort 1, and
- the review of safety/tolerability data through Day 36, including safety clinical laboratory.

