Likewise, the dosing of Cohort 3 participants (body weight 40 to 60 kg inclusive) will proceed only after the satisfactory review of safety and tolerability data from at least [redacted] participants who received at least 5 treatment doses in Cohort 2 as shown in [Figure GPHV.1.1](#). PK samples will be collected, and exposure data for tirzepatide will be analyzed during the study to support dose-escalation decisions where possible. Sentinel dosing will be used for [redacted] participants in the specific body weight range of 40 to 50 kg in Cohort 3 [redacted]. If safety and tolerability after at least 1 week are acceptable in the [redacted] sentinel participants, as clinically assessed by the investigator, the remainder of the participants in Cohort 3 ([redacted] tirzepatide and [redacted] placebo) in the 40 to 60 kg range can be randomized and dosed.

A final follow-up visit will occur within 4 to 6 weeks after last treatment or at least 4 weeks but up to 6 weeks for participants who discontinued prematurely.

Starting at Visit 2 (baseline visit), all participants will be offered intensive behavioral therapy (IBT) sessions (Section [5.3.1](#)) which will continue through the study period and until the final follow up.

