### 6.5.1. Data Review during the Study

Data will be analyzed while the trial is ongoing. An assessment committee will not be formed. Safety data will be reviewed by sponsor on a regular basis while participants are enrolled in the study.

Two safety data reviews are planned to occur during the Study GPHV. Such an interim safety review will not be considered as formal interim analyses. This review will be used to support dose decisions for subsequent cohorts to be enrolled. The interim data reviews will include the following:

- *Cohort 1 safety and tolerability data review*- all available safety and tolerability data up to at least Day 36 from at least [redacted] participants with obesity in Cohort 1 who received and completed at least 5 weeks of treatment, and
- *Cohort 2 safety and tolerability data review*- all available safety and tolerability data up to at least Day 36 from at least [redacted] participants with obesity in Cohort 2 who received and

completed at least 5 weeks of treatment and all available safety and tolerability data from Cohort 1 participants.

At the time of safety reviews, any available PK data may also be reviewed by sponsor.

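### Read literally, enrollment-pause criterion 2 in Protocol 6.5 needs two severe related AEs in one child, but the same section discontinues a child at the first

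*Protocol*

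**What the plan says.** Protocol 6.5 (Dose Modification) contains two lists.

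The first acts on the individual child. Its second item reads: "A severe non-serious AE occurs and is considered at least possibly related to the study intervention occurring in the participant". Its first item does the same for an SAE, and its third covers intolerable GI events. When any item is met, "dosing at the current level and further dosing will be stopped for the participant who will be discontinued".

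The second list acts on the trial. When any criterion is met, "an additional safety review will be initiated and new enrollment will be paused until the safety review is complete".

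- Criterion 1 needs one related SAE in a child on active drug in the cohort.
- Criterion 2 reads: "One or more participants on active drug experience 2 clinically significant severe AEs considered to be related to tirzepatide".
- Criterion 3 opens with "Two or more participants in the cohort experience". It then names severe drug-related GI effects and symptomatic hypoglycemia below 54 mg/dL, joined by *and*.

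There are other safeguards. Under Protocol 6.5.1, "Safety data will be reviewed by sponsor on a regular basis while participants are enrolled in the study". Under Protocol 4.1, the start of Cohort 2 depends on "the review of safety/tolerability data through Day 36, including safety clinical laboratory", and Cohort 3 dosing "will proceed only after the satisfactory review of safety and tolerability data" from Cohort 2. Cohort 3 also has sentinel participants.

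Neither Protocol 6.5.1, the amendment history in Protocol 10.12, nor the SAP (including 10.5.1 on adverse events) says how the two events in criterion 2 are to be counted.

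**The concern.** The two lists should work together: the first protects the child who has the event, and the second protects the children not yet enrolled. If the two events in criterion 2 must fall in one child, the first list removes that child from dosing before a second event would usually arise. The pattern that most suggests a dose is poorly tolerated is one severe related event in each of several children. On that reading, this pattern would not meet criterion 2.

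At stake is whether enrollment of children aged 6 to 11 pauses automatically or only if someone decides that it should. The synopsis provides for no data monitoring committee, and Protocol 6.5.1 says that no assessment committee will be formed, so the written criteria carry more weight than they otherwise would.

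**Working it through.** The plan gives no operating characteristic for the pause rule, so there is no figure to reproduce. The check is one of text and logic, with a short illustration.

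**1. Which reading does the text favor?** Per child: the subject is one or more participants, and they must experience 2 events. Criterion 3 names two or more participants when it means to count children. Pooled: criteria 1 and 3 limit themselves to the cohort and criterion 2 does not, and there is no *each* or *same participant*. The literal sense leans per child. The pooled sense remains open.

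**2. How does criterion 2 meet the individual rules?** An AE judged related is also at least possibly related. If it is serious, individual rule 1 applies; if it is severe and non-serious, individual rule 2 applies. So every event that counts toward criterion 2 also discontinues the child. A second event in that child must come close to the first, before discontinuation takes effect, or after the last dose.

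**3. How much drug remains after the last dose?** Input: a half-life of 5 to 6 days (Protocol 10.2.1.1). With simple exponential decay, the fraction left after *t* days is 2^(−t/half-life).

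| Days after last dose | Half-life 5 days | Half-life 6 days |
|---|---|---|
| 1 | 0.87 | 0.89 |
| 3 | 0.66 | 0.71 |
| 7 | 0.38 | 0.45 |
| 28 | 0.02 | 0.04 |

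A second related event is plausible in the first days and much less so by the follow-up visit, 4 to 6 weeks after the last dose.

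**4. What does each reading require?** Let a_i be the number of clinically significant, severe, related AEs in child i on tirzepatide.

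- Per child: max(a_i) ≥ 2.
- Pooled: sum(a_i) ≥ 2.
- Proposed rewording: at least two children with a_i ≥ 1, or max(a_i) ≥ 2.

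The rewording equals the pooled reading. If the sum is 2 or more, either one child has two events or two children have at least one each, and the converse is immediate. Enumerating 1 to 7 children with a_i from 0 to 3 gives 4 + 16 + 64 + 256 + 1,024 + 4,096 + 16,384 = 21,844 patterns, with no mismatch. The rewording triggers and the per-child reading does not in the sum of (2^n − 1 − n) = 0 + 1 + 4 + 11 + 26 + 57 + 120 = 219 patterns. In all 219, at least two children have exactly one event and no child has two. These counts check the logic; they are not probabilities.

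**5. Illustration on assumed inputs only.** Let n be the number of children on tirzepatide, p the chance that a child has at least one such AE, and q the chance of a second in that child although dosing stops. Children are taken as independent.

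- Per child: 1 − (1 − pq)^n.
- Pooled: 1 − (1 − p)^n − n·p·(1 − q)·(1 − p)^(n−1).

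For n = 12, p = 0.10, q = 0.1: per child, 1 − 0.99^12 = 0.114; pooled, 1 − 0.282 − 0.339 = 0.379.

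| n = 12, p = 0.10 | Per child | Pooled |
|---|---|---|
| q = 0 | 0% | 34% |
| q = 0.1 | 11% | 38% |
| q = 0.3 | 31% | 45% |

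Over n = 6, 12, 18, p = 0.05 to 0.20 and q = 0 to 0.3, the per-child figure runs from 0% to 67% and the pooled figure from 3% to 93%. The pooled figure is higher at every point, but the difference ranges from slight (n = 6, p = 0.05, q = 0.3: 9% against 10%) to large (n = 18, p = 0.20, q = 0: 0% against 90%). None of these is an estimate for this trial.

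**The case against.** The strongest defense is that the two lists set different thresholds on purpose. Stopping one child needs only possible relatedness, which a blinded investigator can judge. Pausing the trial needs clinical significance, relatedness to tirzepatide and knowledge of the allocation. A low bar for one child and a higher bar for the trial is coherent. This stands as a reason why the overlap is not a contradiction. It does not say how the two events are counted.

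A reader might infer that the per-child criterion can never be met, or that only the pooled reading gives both lists a function. The documents do not support either. Severe vomiting and severe diarrhea can arise together, and most of the drug is still present at 1 to 3 days. Remote visits and home dosing can delay awareness, causality can be revised (Protocol 10.3.4), and AEs are collected until participation ends (Protocol 8.3.1). Criteria 1 and 3 work whichever way criterion 2 is read.

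A reader might also infer that these children go unwatched. They do not. The sponsor reviews safety data regularly, and its study team is unblinded (SAP 6). Immediate concerns go to the sponsor at once (Protocol 8). Related cases of severe hypoglycemia (Protocol 8.3.3.3) and diagnosed acute pancreatitis (Protocol 10.6) are SAEs and so meet criterion 1. Criterion 3 reaches beyond GI events, because it names symptomatic hypoglycemia. If its two items are alternatives, the remaining gap is narrower; if both are required, it is wider. What remains is that none of the sponsor reviews, cohort-start decisions or sentinel steps fixes a count at which enrollment must pause within a cohort for the events left to criterion 2.

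**Conclusion.** The concern holds. On its literal reading, criterion 2 works poorly beside the individual discontinuation rule. The number of children who can each have one qualifying event with criterion 2 still unmet is every child on tirzepatide on the per-child reading, against 1 on the pooled reading. The practical gap is severe, related, non-serious AEs in separate children that criteria 1 and 3 do not capture. If the sponsor already applies the pooled reading, there is no gap for events that are clinically significant and judged related to tirzepatide, only an unstated rule.

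That the text leaves the count open is clear. The consequence is not: cohort sizes are redacted in Protocol 4.1 and 9.5, no event rate is given, and Protocol 7.2 expects discontinuation to be uncommon, so the gap may seldom matter. The primary endpoint and its analysis are unaffected. The point deserves correction because it is a safety trigger in a pediatric trial and the remedy is small.

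**What to change.** Replace criterion 2 with wording such as: *Two or more participants assigned to tirzepatide (including any already discontinued) each have at least 1 clinically significant, severe AE judged related to tirzepatide, or one such participant has 2 such AEs.*

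Referring to assignment avoids a further doubt, namely whether a child whose dosing has stopped is still on active drug when a second child has an event. AEs after the last dose should continue to count, and no cohort limit need be added. Criterion 1, the individual rules and SAP 10.5.1 can stay as they are.

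The change is one sentence, but it is a protocol amendment. Under Protocol 10.1.1 it needs ethics approval before implementation, and health authority approval if it is substantial. If pooling was intended, the event count that triggers a pause is unchanged. If per-child counting was intended, there will be somewhat more pauses, only when two or more children have one event each and none has two. Each pause lasts only until the safety review is complete.

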## 2.3. Benefit/Risk Assessment

The risks of tirzepatide have been consistent with risks associated with other GLP-1 receptor agonists currently marketed. Potential risks include, but are not limited to, GI effects, acute pancreatitis (very rare), increases in heart rate, and hypoglycemic events (GLP-1 receptor agonist class effect).

No clinically significant safety or tolerability concerns have been identified during the clinical investigation of tirzepatide up to the single dose level of 5 mg or multiple weekly doses, when escalated up to 15 mg in adults. Based on this information, the highest starting dose of [REDACTED] mg and the highest dose of [REDACTED] mg tirzepatide to be administered in this study are reasonably anticipated to be tolerable in this group of pediatric participants with obesity.

Body weight is a known covariate affecting tirzepatide exposures based on population PK analysis in adult patients with T2DM. It is predicted that the exposure may be approximately 2-fold higher in the population with weight <50 kg compared to that in adults (weight  $\geq$ 50 kg); therefore, a more conservative initial starting dose of [REDACTED] mg will be adopted for participants in the lower body weight cohort (Cohort 2). This is a mitigation approach taken to reduce the risk of safety and tolerability issues before commencing another cohort of participants on an initial [REDACTED]-mg dose (Cohort 3).

Based on the known pharmacology of tirzepatide, participants with obesity may benefit from clinically meaningful weight reduction after 8 weeks of treatment. Potential risks, such as GI effects, acute pancreatitis, increases in heart rate, and hypoglycemic events, are consistent with the risks associated with currently available long-acting GLP-1R agonists in adults. These risks are clinically detectable and manageable and will be monitored throughout the study.

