**Level 2 hypoglycemia:**

Glucose <54 mg/dL (3.0 mmol/L): Level 2 hypoglycemia is also referred to as documented or blood glucose confirmed hypoglycemia with glucose <54 mg/dL (3.0 mmol/L). This glucose threshold is clinically relevant regardless of the presence or absence of symptoms of hypoglycemia.

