**Level 3 hypoglycemia:**

Severe hypoglycemia (in adults): A severe event characterized by altered mental and/or physical status requiring assistance for treatment of hypoglycemia. For example,

participants had altered mental status, and could not assist in their own care, or were semiconscious or unconscious, or experienced coma with or without seizures, and the assistance of another person was needed to actively administer carbohydrate, glucagon, or other resuscitative actions. Glucose measurements may not be available during such an event, but neurological recovery attributable to the restoration of glucose concentration to normal is considered sufficient evidence that the event was induced by a low glucose concentration.

The determination of a hypoglycemic event as an episode of severe hypoglycemia, as defined above, is made by the investigator based on the medical need of the participant to have required assistance and is not predicated on the report of a participant simply having received assistance.

If a hypoglycemic event meets the criteria of severe hypoglycemia, the investigator must record the event as serious on the AE CRF and report it to Lilly as an SAE.

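### Pause trigger 3 in Protocol Section 6.5 joins severe GI effects and symptomatic low glucose by *and*, so read literally a cluster of symptomatic, non-severe, non-serious hypoglycaemia starts no safety review

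*Protocol*

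**What the plan says.** Protocol Section 6.5 has two lists. The first stops an individual child, for one of three reasons: a related SAE, a severe related AE ("A severe non-serious AE occurs and is considered at least possibly related to the study intervention occurring in the participant"), or intolerable GI events.

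The second list starts an additional safety review and pauses new enrolment until the review is complete. Its triggers are:

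- Trigger 1 rests on serious events: "One or more participants in the cohort on active drug experience SAE considered to be related to tirzepatide".
- Trigger 2 rests on severe events: "One or more participants on active drug experience 2 clinically significant severe AEs considered to be related to tirzepatide".
- Trigger 3 sets a count of at least two children per cohort and has two items. Item (a) concerns GI effects attributed to the drug, and its wording, connector included, ends: "severe treatment-emergent AEs causing significant distress or requiring urgent medical interventions beyond routine symptomatic treatment, and". The item that follows, (b), covers "symptomatic hypoglycemic episodes with blood glucose levels of <3.0 mmol/L (54 mg/dL").

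Other sections bear on item (b). Section 2.3 lists among the potential risks "increases in heart rate, and hypoglycemic events (GLP-1 receptor agonist class effect"). Section 8.3.3.3 says of the Level 2 threshold, glucose below 54 mg/dL: "This glucose threshold is clinically relevant regardless of the presence or absence of symptoms of hypoglycemia". For Level 3 only, it adds: "If a hypoglycemic event meets the criteria of severe hypoglycemia, the investigator must record the event as serious on the AE CRF".

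The Synopsis states that there is no data monitoring committee, and Section 6.5.1 that no assessment committee will be formed.

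**The concern.** Item (b) reads like a safety signal in its own right, but the connector makes it count only alongside severe GI effects. If two, four or six children in a cohort had symptomatic glucose below 3.0 mmol/L, with no episode severe or serious and no severe GI event, no stated rule would start a review or hold enrolment. The individual stopping rules would not cover these children either, so stopping drug would rest on the investigator's opinion under Section 7.1.

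This matters because the triggers are the only stated rules that require an unplanned review in a study of children aged 6 to 11 without a monitoring committee. Section 4.3 also expects exposure up to 2-fold higher than in adults for those below 50 kg.

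**Working it through.** The documents state no operating characteristics for these triggers, so there is no figure to reproduce. The point rests on the wording. The probabilities in step 4 are illustrations.

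**Step 1. Apply the triggers as written.**

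| Scenario | Trigger 1 | Trigger 2 | Trigger 3, *and* | Trigger 3, *or* |
|---|---|---|---|---|
| 2, 4 or 6 children with symptomatic glucose <3.0 mmol/L, none severe or serious, no severe GI event | no | no | no | yes |
| One child on active drug with related Level 3 hypoglycaemia | yes | not needed | not needed | not needed |
| Two children on active drug, one severe related GI event each | no | yes, if summed over children | no | yes |

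The first row gives the same answer whether *and* is applied within each child or over the cohort.

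**Step 2. Ask what trigger 3 adds under *and*.** Two children with (a) ordinarily already supply two severe related AEs, which meets trigger 2 if its events are summed over children. Trigger 3 then adds almost nothing. That points to *or* as the intended meaning.

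**Step 3. Look for a resolution elsewhere.** Sections 7.1, 7.2 and 10.1.7 close lists of evident alternatives with *and*. In Section 4.1, however, two bullets joined the same way must both be met before Cohort 2 is dosed. Individual stopping rule 3 in Section 6.5 also uses *and* conjunctively. Section 10.4.1 writes *or* where alternatives are meant. Style therefore does not decide the matter, and nothing else in the protocol or SAP does.

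**Step 4. Illustrate the size.** Assumed inputs: n = 6 or 12 children on active drug in a cohort (the real numbers are blacked out); each child has severe GI effects with probability 0.10, one event per affected child; no SAEs; trigger 2 summed over children. Let G be the number with (a) and H the number with (b), where each child has (b) with probability h. No trigger fires on a cluster when H ≥ 2 and G ≤ 1.

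- P(G ≤ 1) = 0.9^n + n × 0.1 × 0.9^(n−1). This is 0.5314 + 0.3543 = 0.8857 for n = 6, and 0.2824 + 0.3766 = 0.6590 for n = 12.
- P(H ≥ 2) = 1 − (1−h)^n − n × h × (1−h)^(n−1).
- If (a) and (b) are independent, the missed-cluster probability is P(H ≥ 2) × P(G ≤ 1). For h = 0.05 this is 0.0328 × 0.8857 = 0.0290 (n = 6) and 0.1184 × 0.6590 = 0.0780 (n = 12).
- If half of the hypoglycaemic children also have (a), the probability is the multinomial sum over the same event. If all do, H ≥ 2 implies G ≥ 2 and the probability is 0.

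| h | n = 6, independent | n = 6, half overlap | n = 12, independent | n = 12, half overlap |
|---|---|---|---|---|
| 1% | 0.1% | 0.1% | 0.4% | 0.2% |
| 2% | 0.5% | 0.3% | 1.5% | 0.9% |
| 5% | 2.9% | 1.9% | 7.8% | 4.7% |
| 10% | 10.1% | 7.0% | 22.5% | 15.1% |

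Under *or*, every entry is 0.

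**Step 5. Vary one assumption.** Trigger 2 has no cohort limit. If severe GI events are counted over three cohorts of equal size, P(G ≤ 1) falls to 0.4503 (18 children) and 0.1126 (36 children). The independent figures become 0.0328 × 0.4503 = 1.5% (n = 6, h = 5%) and 0.3410 × 0.1126 = 3.8% (n = 12, h = 10%), against 2.9% and 22.5%.

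**The case against.** The strongest reply is that nobody would run the rule literally. The protocol often closes lists of alternatives with *and*, and the literal reading makes trigger 3 nearly redundant, so a sensible reader would treat (a) and (b) as separate triggers. As a statement of intent this is probably right. It does not make the text safe, because the same construction is conjunctive in Section 4.1 and within Section 6.5 itself.

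The second reply is that the gap is narrow, and this stands. Section 4.1 limits the study to children without diabetes. The Schedule of Activities sets glucose checks at bedtime on Days 1 and 2 plus fasting chemistry at laboratory visits; other checks are discretionary or prompted by symptoms. Section 10.3.4 grades as severe an event that interrupts usual activities, so some episodes would count towards trigger 2. Under Section 10.3.2 the investigator may judge an episode serious.

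Other controls exist. Immediate concerns go to the sponsor at once (Section 8), the sponsor reviews safety regularly (Section 6.5.1) and its study team is unblinded (SAP Section 6), cohort progression needs a satisfactory review and Cohort 3 has sentinel dosing (Section 4.1), and dosing can be suspended for safety findings (Section 10.1.4). These limit the harm, but none supplies a threshold for this cluster.

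The third reply is that item (b), unlike (a), requires neither active drug nor relatedness. Standing alone, it could be met by two placebo children. This is correct, and the fix below deals with it.

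A reader might also infer that trigger 2 has a similar hole, on the view that its two severe AEs must fall in one child. The documents do not support that. The text equally allows summing over children, and that reading gives the trigger work to do, since one severe related non-serious AE already takes a child off drug. The unstated counting unit is a missing detail, not an error.

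**Conclusion.** The point holds for trigger 3 as written. Two or more children whose only events are symptomatic, non-severe, non-serious glucose readings below 3.0 mmol/L do not by rule start a review or a pause. This conclusion depends on no assumed rate.

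The practical size is small to moderate and cannot be fixed from the documents. In the illustration it runs from 0 (full overlap with severe GI effects) through 2.9% (6 children, 5% hypoglycaemia, independent) to 22.5% (12 children, 10%, independent), and at 1% hypoglycaemia it is 0.4% or less. Every rate and cohort size is assumed.

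Two stronger conclusions are tempting and should be resisted. One is that the sponsor chose to leave hypoglycaemia outside its safety rules; a drafting slip is the likelier explanation. The other is that severe hypoglycaemia could pass unnoticed; Level 3 events are serious by rule, and one related event on active drug meets trigger 1.

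The wording should be fixed because a safety rule gives the wrong result when followed literally and the correction is short.

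**What to change.** Reword trigger 3 so that each item carries its own count: *two or more participants in the cohort on active drug have (a), or two or more participants in the cohort on active drug have (b)*, keeping the present descriptions of (a) and (b). The active-drug limit matches triggers 1 and 2, can be applied by the unblinded sponsor, and keeps placebo events from causing a pause.

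Optionally, in the same amendment, state that the two severe related AEs in trigger 2 are summed across participants.

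The cost is an amendment with IRB/IEC approval (Section 10.1.1) and an occasional extra pause. In the illustration with 6 children and 5% hypoglycaemia, the chance of any pause rises from 11.4% to 14.3% if the events are independent (2.9 points), to 13.4% with half overlap, and not at all with full overlap. With 12 children and independence it rises from 34.1% to 41.9% (7.8 points). The added pauses are exactly the clusters that the literal rule would miss.
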